### 3 SUMMARY

**This study aims to:**

1. Confirm in a prospective multicenter study of normoalbuminuric type 2 DM patients that the urinary proteome test identifies patients with a high risk for development of microalbuminuria.
2. Demonstrate the clinical utility of the test by showing that aldosterone blockade in high-risk patients can reduce progression to microalbuminuria in comparison to placebo, on the top of standard treatment in a randomized double-blind, placebo-controlled multicenter study.

**Patients:** After screening 2700 patients, 2000 normoalbuminuric type 2 DM patients will be included and will be stratified into an observational- and an intervention group using urinary proteomic test.

Patients who have contraindications to aldosterone blockade will not be included in the study.

**Observational group:** Patients who are classified as being at low risk for progression to diabetic nephropathy (approx. 85%) will enter observational period of at least 104 weeks, dependent on time of baseline visit. These patients will continue to receive usual care at their hospital diabetes clinic or GP with treatment according to standard guidelines

**Intervention group:** Patients who are classified as being at high risk (approx. 15%) will be randomly assigned to the mineralocorticoid receptor antagonist spironolactone 25 mg once daily or placebo therapy in addition to optimal standard therapy. These patients will enter a treatment period of at least 104 weeks, dependent on time of baseline visit.

**Endpoint:** The primary endpoint will be the development of confirmed microalbuminuria (UACR >30 mg/g) in at least two out of three urine tests, with at least 30% increase in UACR from “run-in” period. We will also examine changes in albuminuria throughout the study period in all patients by assessing the slope of albuminuria changes and absolute changes from inclusion to the end of study. We will compare the observational group and the treated intervention group in order to assess the predictive value of the urinary proteomics test. Furthermore, within the intervention group we will compare changes in albuminuria between patients randomized to placebo or the mineralocorticoid receptor antagonist spironolactone. The analysis will consider age and gender effects on the predictive value of the proteomics test and treatment effect.

## 4 BACKGROUND INFORMATION AND SCIENTIFIC RATIONALE

### 4.1 Background Information

Diabetes mellitus (DM) affects 9% of the European population and the cost of caring for patients with DM accounts for 15% of the European health care budget expenditure. Almost 90% of patients have type 2 DM, and absolute numbers are expected to rise in parallel to the current obesity and metabolic syndrome epidemic. Improved treatment has reduced mortality but the prolonged duration of DM increases the likelihood of development of late diabetic complications (1;2).

Diabetic nephropathy is one of the major late complications of diabetes and is associated with substantial cardiovascular morbidity and mortality and is a leading cause of end stage renal disease (ESRD) in the Western world (1). In clinical practice, renal impairment is diagnosed by albuminuria or proteinuria and/or changes in serum creatinine/creatinine clearance indicating alterations of the glomerular filtration rate (GFR) (3). However, the inter-individual variability is high, and as a consequence, these standard tests have a moderate specificity and sensitivity at early stages of disease, with major limitations in the diagnosis of the early stages of diabetic nephropathy (DN) (4).

Development of DN is generally characterized by an increase of urinary albumin excretion rate (>300 mg/24 h or 200 µg/min). Microalbuminuria (30-300 mg/24 h or 20-200 µg/min) is considered a risk factor and as an early indicator of future onset of DN. Microalbuminuria is regarded as the earliest clinical marker of renal damage (5;6). However, structural changes to the kidney have already occurred at the stage of microalbuminuria and patients with microalbuminuria have a high risk for development of renal disease, but also increased morbidity and mortality due to cardiovascular disease (7;8).

Blood pressure and glycemic control with pharmacotherapeutic intervention as well as life style interventions are the cornerstones of type 2 DM management aiming at prevention of microvascular complications (9;10). Specific therapy, particularly treatment with angiotensin converting enzyme inhibitors (ACE) and angiotensin receptor antagonists (ARB) to prevent progression to overt proteinuria and advanced stages of diabetic nephropathy is recommended if microalbuminuria is present (11;12). Studies aiming for earlier prevention of nephropathy by starting renin angiotensin aldosterone system (RAAS) blocking treatment in normoalbuminuric patients have given mixed and often disappointing results (13). This might reflect that a large fraction of normoalbuminuric patient may not be at risk for progression thereby reducing the event rate or power in previous studies (14). Early identification of normoalbuminuric patients at high risk for development of diabetic nephropathy could identify patients who might benefit of intervention with increased blockade of the RAAS. Furthermore, blockade of the RAAS with aldosterone blockade has been demonstrated to reduce urinary albumin excretion with 20-30% on top of standard anti-hypertensive treatment including ACE or ARB in proteinuric type 1 and 2 diabetic patients, and a 60% reduction was seen in microalbuminuric type 1 diabetic patients (15;16). Therefore, it may also hold the potential to reduce the risk of development of microalbuminuria in high risk normoalbuminuric patients.

### CKD Biomarker panel

Proteomics is the analysis of large number of proteins or polypeptides in tissue and body fluids. Capillary electrophoresis-mass spectrometry (CE-MS) enables reproducible and robust high-

resolution analysis of several thousand low-molecular-weight urinary proteins/peptides in about one hour (17). Urine holds several advantages over blood in clinical proteomics. It can be collected non-invasively and its proteome is relatively stable (18). Members of the consortium have successfully identified a urinary biomarker pattern including 273 peptides significantly associated with chronic kidney disease (CKD273) (19).

Importantly, the biomarker panel has been validated in a multicentric approach involving >1000 blinded samples (20;21). The accuracy was high (96% sensitivity and 98% specificity), when evaluating only the diabetic patients in the test-set. To test the CKD273 pattern as a tool for early detection of DN, we recently performed an independent longitudinal study of normoalbuminuric diabetic patients at inclusion (22). The urinary CKD273 pattern distinguished progressing patients from non-progressing patients. The corresponding receiver operating characteristic (ROC) analysis resulted in an area under the curve (AUC) of 0.925 assuming a prevalence of 30% for DN. The positive predictive value was 97% and the negative predictive value was 88%. The specificity of the CKD273 pattern was further evaluated in patients without any evidence for renal impairment based on clinical history, creatinine, or urinary protein levels resulting in an overall specificity of 98%.

The used CKD273 pattern showed that these biomarkers can detect initiation and progression of DN earlier than the currently used indicators, well preceding increases in urinary albumin levels. While the CKD273 pattern detected DN with >90% accuracy four years before clinical diagnosis, serum creatinine and/or UAER did not detect DN earlier than one and two years before clinical manifestation, respectively. In addition, diagnostic accuracy was significantly lower compared to the CKD273 pattern. In addition, two independent studies on type 1 and type 2 DM patients, on longitudinally collected samples over a period of 10 years demonstrate that CKD273 markers of kidney disease were altered 3 to 5 years prior to manifestation of albuminuria, and 1 to 2 years prior to development of microalbuminuria (22;23). Thus, the performance of the CKD273 pattern is better than prediction based on urinary albumin values and represents potentially a significant improvement over the current state of the art in assessing DN, enabling earlier detection with higher accuracy than urinary albumin (24).

Finally, the proteome analysis and application of the CKD273 pattern indicated a positive scoring for CKD in microalbuminuric type 2 diabetic patients, which showed persistent improvement during long-term renoprotective treatment with Irbesartan, while placebo treated patients showed a slight deterioration of kidney damage markers likely reflecting disease progression in the absence of pre-emptive intervention (25).

Collectively, our existing data strongly indicate that the urinary proteomics based test appears ideal to identify patients who will develop microalbuminuria and ultimately DN and thereby facilitates targeting intensified preventative therapy to this group.

## 4.2 Rationale

1. Urinary proteomics predicts development of microalbuminuria (as a surrogate marker for the development of overt nephropathy) in a cohort of 2000 type 2 diabetic patients with normal urinary albumin excretion at screening.
2. Early initiation of preventive therapy with spironolactone reduces risk of transition to microalbuminuria in those identified by urinary proteomics to be at high risk, and thereby delays progression to overt nephropathy. Treatment can be spared for those with low risk according to urinary proteomics, paving the way of personalised medicine

## 5 OBJECTIVES AND ENDPOINTS

### 5.1 Primary objective

To confirm that urinary proteomics can predict development of microalbuminuria (as a surrogate marker for the development of overt nephropathy) in a cohort of 2000 type 2 diabetic patients with normal urinary albumin excretion.

### 5.2 Secondary objectives

To investigate if early initiation of preventive therapy with spironolactone 25 mg once daily reduces risk of transition to microalbuminuria in those patients identified by urinary proteomics to be at high risk.

### 5.3 Additional scientific objectives

To compare the rate of change in urinary albumin excretion rate in high vs. low-risk population (based on the proteomic test), and to compare the effect of spironolactone on rate of change in UACR in the intervention group.

In addition, the objective is to study the rate of change in eGFR (26) in relation to urinary marker pattern (CKD 273) and the intervention with spironolactone.

To study the ability of urinary proteomic patterns, to predict cardiovascular or renal events during the study as well as response to intervention, in relation to study endpoints.

A research biobank will be established at Steno Diabetes Center containing biological material in the form of blood and urine samples. This will allow testing of additional putative markers for progression of diabetic nephropathy and development of cardiovascular events and death (such as but not limited to): Endothelial dysfunction (vWF, ADMA, VCAM, ICAM, E-selectin), inflammation (hs-CRP, IL-6, TNF-alpha, YKL40, IL-8, IL10), vascular riskmarkers (NT-proBNP, adiponectin, ghrelin), and bonemarkers (vitamin D, p-PTH, p-calcium, p-phosphat, p-magnesium, osteoprotegerin (OPG), osteopontin (OPN), RANKL, bone morphogenic protein (BMP), p-FGF23, osteocalcin, bone-specific alkaline phosphatase).

### 5.4 Primary endpoint

Development of confirmed microalbuminuria (UACR >30 mg/g) in at least two out of three first morning voids with  $\geq 30\%$  increase (geometric mean) in UACR from "run-in" period samples OR > 40 mg/g (geometric mean).

### 5.5 Secondary endpoints

#### 5.5.1 In the total population:

In the following paragraphs patients in the intervention group, (group B) and observation group (group A) will be compared.

- Comparison of composite fatal and non-fatal cardiovascular outcome (MI, stroke, CABG, PTCA, hospitalization for heart failure and CVD), and all-cause mortality during the study.

- Comparison of incidence of retinopathy and frequency of laser treatment. Data collected from self-reported AEs
- In addition to the categorical analysis of urinary albumin excretion, an analysis will be performed with changes in geometric mean albuminuria throughout the study period in all patients by assessing the slope of albuminuria changes and absolute changes from inclusion to end of trial
- Development of microalbuminuria (UACR >30 mg/g) in at least one morning void urine sample will be used as a secondary outcome instead of confirmed microalbuminuria
- Development of macroalbuminuria (UACR >300 mg/g in 2 out 3 first morning void urine samples)
- For patients with eGFR  $\geq 60$  at baseline, development of eGFR <60 ml/min/1.73m^2.
- Change in eGFR (slope and absolute from baseline and from 3 month post-baseline to end of study)

### **5.5.2 In the intervention group (group B) / High-risk population:**

In the following paragraphs patients receiving active medication will be compared to placebo treatment.

- Comparison of composite fatal and non-fatal cardiovascular outcome (MI, stroke, CABG, PTCA, hospitalization for heart failure and CVD) and all- cause mortality during the study.
- Comparison of incidence of retinopathy and frequency of laser treatment. Data collected from AEs
- Development of microalbuminuria (UACR > 30 mg/g) in at least one morning void urine sample will be used as a secondary outcome instead of confirmed microalbuminuria
- Development of macroalbuminuria (UACR > 300 mg/g in 2 out 3 first morning void urine samples)
- For patients with eGFR  $\geq 60$  at baseline, development of eGFR <60 ml/min/1.73m^2
- Change in eGFR (slope and absolute from baseline and from 3 month post-baseline to end of study)

## **5.6 Assessment of Safety**

The assessment of safety will be based primarily on the frequency of eCRF-documented AEs, laboratory abnormalities, and SAEs (see section 13.2.). Occurrence and frequency of eCRF-documented AEs, SAEs and laboratory abnormalities will be summarized by treatment group.

In addition AEs leading to death and AEs leading to discontinuation of study medication and/or withdrawal will be summarized for the two treatment groups.

## **5.7 Calculation of eGFR**

Calculation is based on locally measured creatinine from a blood sample. At the time of screening the local eGFR will be used for evaluation of inclusions criteria no. 5 only.

[figure not shown]
Information in the eCRF is based on the creatinine measurement method in the local laboratory. The central calculation of eGFR will be made with CKD-EPI equation. The estimation will be made centrally in the eCRF after entry of creatinine data by the investigators.

CKD-EPI equation:  $GFR = 141 \times \min(Scr/\kappa, 1)^\alpha \times \max(Scr/\kappa, 1)^{-1.209} \times 0.993^{Age} \times 1.018$  [if female]  $\times 1.159$  [if black]. Where Scr is serum creatinine (mg/dL),  $\kappa$  is 0.7 for females and 0.9 for males,  $\alpha$  is  $-0.329$  for females and  $-0.411$  for males, min indicates the minimum of Scr/ $\kappa$  or 1, and max indicates the maximum of Scr/ $\kappa$  or 1.

The information in the eCRF on eGFR will be used as safety measures throughout the study.

## 6 STUDY DESIGN

Figure 1: Trial flow chat

## 6.2 Observation group (group A) / Low-risk population

It is expected that 85% of the total population (approx. 1700 patients) will show a low-risk pattern. Patients should be followed by the investigator in routine clinics or seen once yearly, for standard diabetes care according to local guidelines. Annual measurements of UACR, BP, medication, and locally measured creatinine, sodium, potassium, and lipids (cholesterol, HDL, LDL, triglycerides) will be performed. HbA1c will be measured in DCCT-aligned quality control programs or IFCC. During the study, the medical history regarding vascular events, current retinopathy status (by history) and information on laser treatment, as well significant medical events (see section 10.14.), including hospital admissions, are registered.

Secondary endpoints and significant medical events will be registered at the annual visits.

After the last study visit, patients will continue in the observational long-term follow-up in accordance with section 6.4.

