### 7.1 Inclusion Criteria

- 1) Written informed consent must be provided before participation. Patient information and consent form must be approved by relevant independent EC. Specifically, all participating patients will be asked to give informed consent for long-term follow-up
- 2) Male or female patients  $\geq 18$  years and  $< 75$  years of age at Screening visit
- 3) Type 2 DM (WHO criteria)
- 4) Persistent normoalbuminuria (at least 2 of 3 UACR  $< 30$  mg/g samples from "run in"-period)
- 5) eGFR  $> 45$  ml/min/1.73m^2 at Screening visit
- 6) The patient must be willing and able to comply with the protocol for the duration of the study
- 7) Female without child-bearing potential at the screening visit. Defined as one or more of following:
  - 7.1) Female patients  $\geq 50$  years of age at the day of inclusion, who have been postmenopausal for at least 1 year
  - 7.2) Female patients  $< 50$  years of age at the day of inclusion, who have been postmenopausal for at least 1 year and serum FSH levels  $> 40$  mIU/mL as well as serum estrogen levels  $< 30$  pg/ml or a negative estrogen test.
  - 7.3) 6 weeks after surgical sterilization by bilateral tubal ligation or bilateral ovariectomy with or without hysterectomy.  
OR a negative urine pregnancy test at the Screening visit AND one or more of following:
  - 7.4) Correct use of reliable contraception methods. This includes one or more of the following: hormonal contraceptive (such as injection, transdermal patch, implant, cervical ring or oral) or an intrauterine device (IUD) OR correct use of double barrier with one of the following: barrier methods (diaphragm, cervical cap, Lea contraceptive, femidom or condom) AND in combination with a spermicide.
  - 7.5) General sexual abstinence from the time of screening/ during the study until a minimum of 30 days after the last administration of study medication if this is already established as the patient's preferred and usual lifestyle.
  - 7.6) Having only female sexual partners.
  - 7.7) Sexual relationship with sterile male partners only.

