#### **14.6 Criteria for discontinuation**

A participant must be discontinued in the IMP treatment if any of the following is present:

- Female patients in the intervention study who become pregnant, intend to become pregnant or do not use adequate birth control (according to inclusion criteria 7, in section 7.1).
- Experience of research-related injury or unacceptable side effects to the study medication.
- Safety considerations assessed by the investigator
- Treatment with Lithium (ATC: N05AN).
- Treatment with potassium sparing diuretics (ATC: C03D, C03E).
- Confirmed eGFR below 15 ml/min/1.73 m^2.
- Confirmed elevated liver enzyme (ASAT and/or ALT) 3 times above normal range.

Discontinued patients will be offered tests corresponding to the final study visit. Data on all patients will be included in the study and will be used in safety analysis.

After discontinuation of study medication in the randomized population, observation should continue with visits as planned in the observational group (if the patient accepts), or if that is not possible/acceptable, evaluation of vital status and development of endpoints should be evaluated through registries, information of hospitals and GPs, or interviews with the patient as appropriate and possible in order to monitor development of endpoints in all included patients as thoroughly as possible, provided that the patient agrees.

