5.4 Withdrawal/ follow-up

Time of follow-up will be estimate from baseline to end – exposure time measure in day/years. Participants who withdraw will be included in the analysis with exposure time from baseline to last observation. Participants who withdraw consent are included in the statistical analysis unless they specifically also withdrawal consent to use of data already entered in the eCRF.

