6.1.2 Secondary outcome

- A. Comparison of composite fatal and non-fatal cardiovascular outcome (MI, stroke, CABG, PTCA, hospitalization for heart failure and CVD) and all-cause mortality during the study.
- B. Comparison of incidence of retinopathy and frequency of laser treatment. Data collected from self-reported AEs.
- C. In addition to the categorical analysis of UACR, an analysis will be performed with changes in geometric mean of UACR throughout the study period in all patients by assessing the slope of albuminuria changes and absolute changes from inclusion to end of trial.
- D. Development of microalbuminuria (UACR >30 mg/g) in at least one morning void urine sample will be used as a secondary outcome instead of confirmed microalbuminuria.
- E. Development of macroalbuminuria (UACR >300 mg/g) in 2 out 3 first morning void urine samples).
- F. For patients with eGFR ≥ 60 ml/ min/ 1.73 m² at baseline, development of eGFR <60 ml/min/1.73m².
- G. Development of CKD stage 4 (eGFR <30 ml/min/1.73m²).
- H. Change in eGFR (slope) from baseline and from three-month post-baseline to end of study.
- I. Change in eGFR (40 % reduction) from baseline and from three-month post-baseline to end of study.
- J. Safety: Adverse Events and Serious Adverse Events. Adverse Events leading to death or discontinuation of study medication and/or withdrawal.
- K. Event of hyperkalaemia with potassium level in plasma ≥ 5.5 mmol and/or ≥ 5.8 mmol in serum at any time point.

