6.3.1.2 Analysis of secondary endpoints

Based on a 2x2 table included the primary endpoint (event/ event free) vs. risk stratification ("high"/- "low"-risk) we will calculate sensitivity, specificity and numbers need to screen for CKD273 and tested for significance using Chi-square test. In a logistic model we will added value using AUC and ROC with comparison between "high"- and "low"-risk vs. event and event-free for both primary endpoint. The logistic models will be performed both unadjusted and adjusted for age, gender, HbA_{1c}, systolic blood pressure, retinopathy, eGFR and UACR at baseline.

For the Cox-regression model a model, including adjustment for age, gender, Hba1c, systolic blood pressure, retinopathy eGFR and UACR at baseline will be comprised for secondary endpoints (see section 6.1.1 and 6.1.2, excluding 6.1.2 C, H and J).

For further clarification of the added value for discrimination, the rIDI will be calculated based on all above described Cox-regressions models with a significant HR for CKD273 in the unadjusted model for each endpoint.

To evaluate changes in UACR and eGFR over time (outcome measurement C and H in section 6.2.1) a linear mix model will be applied with adjustment for eGFR and UACR at baseline.

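### In-trial tracing of deaths and cardiovascular events is specified only for randomised (high-risk) patients, so the high- versus low-risk comparison of outcome A rests on unequal ascertainment

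*Protocol*

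**What the plan says.** **Low-risk patients (group A).** Protocol 6.2 states that "Secondary endpoints and significant medical events will be registered at the annual visits". Protocol 10.14 likewise places documentation of significant medical events at the annual visit, and Table 1 adds an end-of-study or early-termination visit.

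**High-risk patients (group B).** Protocol 6.3 registers secondary endpoints every 13 weeks. Protocol 14.6 adds: "After discontinuation of study medication in the randomized population, observation should continue with visits as planned in the observational group". If that is not possible or acceptable, "evaluation of vital status and development of endpoints should be evaluated through registries, information of hospitals and GPs", or patient interviews, as appropriate and if the patient agrees. The sentence closes with the aim of monitoring endpoints in everyone included.

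**The comparison.** Protocol 5.5.1 introduces its list with "In the following paragraphs patients in the intervention group, (group B) and observation group (group A) will be compared", and the list begins with the cardiovascular composite and all-cause mortality. In SAP 6.1.2 this is outcome A, which includes "all-cause mortality during the study". SAP 6.3.1.2 fits Cox models to the secondary outcomes in the observational cohort, "excluding 6.1.2 C, H and J", so outcome A is included.

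**Follow-up time.** SAP 5.4 states: "Participants who withdraw will be included in the analysis with exposure time from baseline to last observation". SAP 6.2 says that no data will be censored.

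**The concern.** The only in-trial instruction to look for endpoints outside study contact starts from stopping study medication. A low-risk patient takes none, so the instruction cannot be triggered in group A. Two patients who both stop attending can therefore be handled differently. The randomised one may have a later death or infarction found in a register, while for the low-risk one the plan names no source.

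Predicting cardiovascular and renal events from CKD273 is a stated additional objective (Protocol 5.3, SAP 2.3.3). If leavers are sicker than stayers, tracing adds high-event-rate time to the high-risk group only, and the hazard ratio moves in the direction that favours the test. Adjusting for baseline covariates does not repair this, because the difference lies in which events are recorded.

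**Working it through.** **1. Does any other provision cover group A?**
- Protocol 14.5 asks for all efforts to complete observations when any patient withdraws. It names no register, hospital or GP source and does not mention vital status after withdrawal.
- Protocol 6.4 describes register follow-up for both groups, but 5 years after the trial and outside the eCRF. Outcome A is confined to the study period.
- SAP 6.3.1.3 carries interim primary endpoints forward to the next annual visit, and SAP 6.4 adds a model on annual samples only. Both concern visit or sampling frequency, not tracing.
- SAP 5.4 ends exposure at the last observation but does not say whether a register date is one.

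None of these removes the asymmetry.

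**2. How large could it be?** The plan states no figure for outcome A, so there is none to reproduce. Every input below except the follow-up length and group sizes is an assumption:
- Share leaving, q: 10% or 15%. Protocol 15.1 and SAP 3.4 (10%) and Protocol 15.6 (under 15%) state these for randomised patients. Using them for group A is an assumption.
- Leaving times spread evenly over each patient's follow-up of 2 to 4.4 years, so a share w = q/2 of follow-up falls after leaving.
- Event rate after leaving: k times the rate before, with k = 1 to 4 (no source in the documents).
- Share of high-risk leavers traced: c. Low-risk leavers traced: none.
- No true CKD273 effect.

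The low-risk rate, ended at leaving, is r. The high-risk rate is r × R, ignoring depletion by the events themselves, where

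R = (1 − w + c·w·k) / (1 − w + c·w)

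For example, with q = 10%, k = 2 and c = 1: (0.95 + 0.10)/1 = 1.050. With c = 0.5: (0.95 + 0.05)/0.975 = 1.026.

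| q | c | k = 1 | k = 2 | k = 3 | k = 4 |
|---|---|---|---|---|---|
| 10% | 0.5 | 1.000 | 1.026 | 1.051 | 1.077 |
| 15% | 0.5 | 1.000 | 1.039 | 1.078 | 1.117 |
| 10% | 1 | 1.000 | 1.050 | 1.100 | 1.150 |
| 15% | 1 | 1.000 | 1.075 | 1.150 | 1.225 |

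A simulation with an assumed death rate of 1.5% per year gives slightly lower values for k = 2 to 4: about 1.02 to 1.11 at c = 0.5 and 1.05 to 1.21 at c = 1. With equal tracing in both groups the ratio is 1.00 whatever q and k are.

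**3. Against the precision available.** At 1.5% per year, the mean follow-up of 3.2 years (the midpoint of 2 and 4.4) gives 300 × 3.2 × 0.015 = 14.4 high-risk deaths and 1700 × 3.2 × 0.015 = 81.6 low-risk deaths. The standard error of the log rate ratio is √(1/14.4 + 1/81.6) = 0.286, so the 95% interval spans a factor of exp(1.96 × 0.286) = 1.75 each way. The shift is modest beside this, but it is systematic.

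**4. Leavers in group A.** 10% to 15% of 1700 is 170 to 255, if the randomised drop-out figures carry over.

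**The case against.** Several points against the concern have weight.

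- *Tracing is a fallback.* The trigger in 14.6 is stopping study medication, not missing visits. Its first instruction puts the patient on the observational group's schedule, which aligns follow-up. Tracing comes only after that, and it depends on feasibility and agreement. This stands, so full tracing is an upper case.
- *Group A is not abandoned.* Protocol 6.2 has these patients followed in routine clinics or seen yearly, with vascular events and admissions registered, and Table 1 gives them an early-termination visit. A reader might infer that a low-risk patient who stops attending contributes nothing afterwards, and that late events exist in one group only. The documents do not support that. They name no tracing route for group A, but they do not forbid one.
- *The purpose clause in 14.6 refers to all included patients.* It may show intent, but no procedure for group A follows from it.
- *SAP 5.4 may already end time at the last attended visit.* If so, traced events would drop out of both groups and this bias would disappear. The text does not say so. That reading would also remove every death from outcome A, since a death necessarily falls after the last attended visit.
- *The stakes are limited.* Outcome A is one of eleven secondary outcomes. Under SAP 4.1 its p-value is calculated only if the primary analysis is significant.

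**Conclusion.** The gap is real: followed as written, the plan ascertains deaths and cardiovascular events after leaving by a specified route in the high-risk group and by none in the low-risk group, and it then compares the two. The direction is towards CKD273 appearing predictive, provided that leavers carry more risk than stayers.

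A reader might infer that the hazard ratio must exceed 1 or that the bias is large. Neither follows. The ratio is 1.00 if leavers have the same risk as stayers, about 1.02 to 1.11 if their risk is two to four times higher and half of high-risk leavers are traced, and up to about 1.2 with full tracing. These figures rest on an assumed death rate, assumed risk multipliers, no tracing at all in group A, and drop-out figures stated for randomised patients. The documents supply no basis for a firmer size. The primary endpoint depends on urine samples and is not affected. This is a cheap improvement to a secondary comparison.

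**What to change.** 1. Extend the last paragraph of Protocol 14.6 to group A. For every included patient who stopped attending, in either risk group, check vital status and outcome-A events through the same sources and to one common cut-off date, subject to consent and national rules. Protocol 7.1 already provides that "all participating patients will be asked to give informed consent for long-term follow-up", and Protocol 6.4 bases that follow-up on register data.
2. In SAP 5.4, define the last observation for outcome A to match, and state whether a traced event counts. Reconcile this with the no-censoring statement in SAP 6.2.
3. In SAP 6.3.1.3, add a sensitivity analysis of outcome A, high versus low risk, that excludes events found only by tracing and censors those patients at last contact.

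Do not instead cut outcome A at the last attended visit, because that would remove all deaths.

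The cost is a one-off record or register check for low-risk leavers, about 170 to 255 patients on the assumption above, across the 15 sites in 10 countries listed in SAP 5.3.3, where access rules may differ. The SAP changes are a few sentences and one extra model.
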